injected. If both eyes have the same acuity the eye with longest onset will be injected. If one eye has <12 months and >6month since onset and the difference in acuity between the eyes is ≤ 10 letters, the eye with ≥ 12 months will be injected. If eyes have an acuity difference >10 letters, the eye with worse acuity will be injected.

Aim 2. To Evaluate the Safety of AAV-ND4 in subjects with acute (<12 months) bilateral loss of visual acuity to ≤ 35 ETDRS letters (Snellen = 20/200) (Group 2). The eye with worse acuity will be injected.

Aim 3. To Evaluate the Safety of AAV-ND4 in subjects with unilateral loss of acuity to ≤ 35 ETDRS letters, but who have “good acuity” ≥ 70 letters (20/40 Snellen) in the contralateral eye (Group 3). The eye with better acuity will be selected for injection.

For each group, administration of study drug will follow an adaptive plan to identify the maximum tolerated dose. If none of the three subjects at a given dose level develops a major toxicity, the next cohort will receive the next higher dose. We will wait a minimum of 6 weeks between injections of the same dose in successive subjects, and will wait until 3 months after the last subject is injected with this dose before moving to the cohort receiving the next higher dose. We will test the lowest dose first in 3 subjects of Aim 1, before moving on to testing this low dose in Aim 2, then lastly in Aim 3. Safety will be monitored for loss of 15 letters in Aims 1 and 2, but a difference of 15 letters worse in the treated eyes relative to untreated eyes for Aim 3. If acuity, and visual field testing demonstrate no toxicity in Aims 1 and 2, we will proceed with Aim 3.

The **objective** of this proposed clinical trial is to evaluate the safety of mitochondrially targeted ND4 gene therapy with the adenoassociated viral vector in appropriate LHON patients in a Phase I clinical trial. If warranted by the results of the Phase I trial, another aim will be to obtain a preliminary estimate of the therapy’s efficacy. We provide a summary of the extensive preclinical testing in relevant rodent animal models to support the efficacy of the approach proposed in this clinical trial.

The **primary hypothesis** being tested is there will be no systemic toxicity or loss of vision to No Light Perception in the injected eye.

4) **Background***

Background and Significance

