Leber’s Hereditary Optic Neuropathy (LHON) is a maternally inherited form of bilateral optic neuropathy causing severe and permanent visual loss in young adults, usually between the second and fourth decades of life. LHON

usually presents as a loss of central vision that typically progresses over weeks without pain, until bilateral central scotomas and visual loss remain. Visual loss may occur in both eyes simultaneously, or in one eye with the fellow eye affected weeks to months later. The deterioration of vision may progress over several months to a maximum loss of function which stabilizes at visual acuities worse than 20/200.

Characterization of the hereditary nature of LHON led early researchers to postulate that it was a disorder of mitochondrial inheritance. Molecular analysis has confirmed that the basic etiology results from a point mutation in mitochondrial DNA (mtDNA). Three primary mutations at nucleotide pair 3460, 11778, and 14484 are generally agreed to be the primary causes of LHON, accounting for 98% of LHON cases. All primary LHON mutations alter mtDNA-encoded protein subunits, which comprise NADH-ubiquinone oxidoreductase (complex I) of the mitochondrial respiratory chain. Therefore, it is generally hypothesized that a dysfunctional respiratory chain impairs ganglion cell function leading to ganglion cell layer and optic nerve damage resulting in vision loss. While the relationship between genotype and phenotype appears straightforward, the selective clinical presentation observed in LHON patients indicates a complex pathogenesis. Although a primary LHON mutation is necessary for the expression of the disease, it is unclear how the mutations interact with other genetic and/or epigenetic factors to cause tissue specific disease in only select individuals.

To date an effective treatment for LHON has not been identified. Anecdotal reports of treatment efficacy have been difficult to interpret given the potential for spontaneous recovery in certain genotypes. Treatments including systemic steroids, hydroxycobalamin, cyanide antagonists, and naturally occurring cofactors (e.g., coenzyme Q10, succinate and idebenone) have not produced definitive evidence of treatment or prevention of visual loss.

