9. History of neurodegenerative conditions (e.g. multiple sclerosis, neuromyelitis optica, Parkinson disease)
10. History of autoimmune conditions (e.g. systemic lupus erythematosus)
11. Systemic diseases having ocular manifestations likely to confound assessment of study resultsHistory of cancer within five years other than localized basal or squamous cell carcinoma not near the orbital area. Patients with a prior history of cancer will need documentation from their cancer specialist that the cancer was cured at least 5 years before study entry.
12. Allergy to pupil dilating drops or narrow angles precluding safe dilation.
13. No Light Perception (NLP) vision in either eye.

, “No special populations are to be included in this research, such as children 14 years old or younger, prisoners, or pregnant women.

- **Exclude:** All subjects who are unable to consent
- **Exclude:** Children 14 years old or younger
- **Exclude:** Pregnant women

- **Exclude:** Prisoners

6) **Number of Subjects***

Number of Study Centers: One (1), Bascom Palmer Eye Institute, University of Miami, Miami, FL.

For each group patient recruitment will consist of 3 cohorts, until the last cohort which will consist of both Group I and III individuals.

Table 1 Proposed Sample Size

	Low-dose (1.18×10^9 vg)*	Medium dose (5.81×10^9 vg)*	High dose (2.40×10^{10} vg)	Higher dose (1×10^{11} vg)
Group I	3	3	3	
Group II	3	3		3
Group III	3	3		
Group I And** Group III				3 3

*=based on CHOP titers as recommended by FDA

As summarized above, dose escalation will follow the adaptive Phase 1 plan of Rubinstein and Simon (<http://linus.nci.nih.gov/techreport/phaselctd.pdf>). At each dose, escalation will occur until 2 of 3 (or 6) injected eyes manifest the safety endpoint. (See reference for detailed description of dose escalation strategy) Table 2 of the reference contains operating characteristics of this approach. Following the algorithm of Rubinstein and Simon with three doses, the sample size could range between 3 and 18 for each group. As an example, if the true probabilities of noteworthy safety events in the proposed three doses were 0.05, 0.25, 0.5, respectively, the most likely sample sizes for each group would range between N=9 with probability 20%, N=12 with probability 54%, or N=15, with probability 22%. These sample sizes could potentially be sufficient to observe a treatment effect when compared in a matched fashion to the uninjected eyes in groups 1 and 3.

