Retinal detachment	Localized and intervention not indicated	Not resolving but intervention not yet indicated	Operative intervention indicated	Operative failure threatening ocular integrity*

*

For group III, due to the natural history of LHON where visual loss is expected in the asymptomatic eye, a vision-related SAE will be considered a decrease in acuity in the injected eye to 0.3 logMAR units (15-letter equivalent) worse than the worst acuity measured in the uninjected fellow eye at the current or any prior study visit.

Table 6-7: Systemic toxicity scale

Grade	Definition
1	Mild toxicity, usually transient, requiring no special treatment and generally not interfering with usual daily activities.
2	Moderate toxicity which may be ameliorated by simple therapeutic maneuvers, and impairs usual activities.
3	Severe toxicity which requires therapeutic intervention and interrupts usual activities. Hospitalization may or may not be required.
4	Life-threatening toxicity which requires hospitalization.

Evaluation of Secondary Endpoint – Visual Function Changes

Visual function will be quantified prior to and after vector administration in order to determine whether vector administration affects visual

function. The main measure of visual function will include best corrected ETDRS visual acuity.

10) Procedures Involved*

Method of Assigning Subjects to Treatment Groups:

Subjects enrolled in the study will be assigned to disease groups based on disease manifestation and screening evaluation. All subjects in the study will receive active treatment (one injection of scAAV2-P1ND4v2) at the Low, Medium or High dose as explained in section 6, Number of Subjects.

Study Visits:

Table 6-4 outlines the schedule of planned study evaluations. Subjects will be enrolled and undergo baseline assessments prior to Day 0. Study agent administration which will occur on Day 0 and details of the procedure are included below.

Table 6-4 Study Visit Summary Procedures

Time point	Baseline		Day								Year				
	B1	B2	0	1	7	3	6	9	1	2	3	1.5	2	3	4-10
Informed consent/assent	■														
Blood test for G11778A mutation	■														
History and physical exam	■			■		■		■			■				
Electrocardiogram, chest X-ray		■													
Pregnancy test	■	■													
Vital signs monitoring	■	■	■	■											
Hematology, chemistry, urinalysis	■		■	■	■	■	■	■	■	■	■	■	■	■	■
Coagulation Panel		■													
AAV antibody and specific reactivity (ASR) measurement	■			■				■			■				

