- In 2001, Bascom Palmer began an intensive recruitment effort to build its research program. There are currently 21 research faculty members in the department. Hiring continues, including scientists and clinician-scientists for the research program, as well as clinicians to staff the expanding clinical facilities.
- The **Anne Bates Leach Eye Hospital** is Bascom Palmer's main facility for ophthalmic care. Operating within a six story building located on the medical campus (opened in 1976), the hospital serves individuals of all ages. More than 200,000 patients are seen each year and at least 10,000 surgical procedures are performed. Additionally, 24-hour emergency care and community-based ophthalmic care for indigent and low-income patients of Miami is provided. The hospital employs numerous optometrists as well as other professional staff.
- The neuro-ophthalmology clinic is run 5 days a week. 3 of these days are staffed by [REDACTED] one of these days staffed by [REDACTED] Therefore we have coverage 80% of the time of every week for our LHON patients. Bascom Palmer

mint maintains a fully staffed eye emergency room 24/7. Therefore we have coverage for any conceivable problem that could arise.

The manual of procedures delineates the protocol to be followed by all personnel in the study. [REDACTED] have just completed a five-year study of patients with LHON that included all evaluations proposed here with the exception of the intravitreal injections of study drug.

23) Prior Approvals

University of Miami Institutional Review Board, University of Miami Biosafety Committee and University of Miami Environmental Health and Safety Department.

Approvals from the Federal Drug Administration and National Institutes of Health/National Eye Institute have been obtained by Sponsor-Investigator, [REDACTED]

24) Recruitment Methods

Patients in this single center study will be recruited from the existing LHON patient pool [REDACTED], where access to records is already given outside of research, and from referrals of outside ophthalmologists. This is the same strategy used to recruit patients for the completed natural history study of Leber's Hereditary Optic Neuropathy (references below). Sufficient participants (N>40) were recruited in this way, even without the possibility of offering participants the possibility of an active treatment. We do not anticipate the need for advertisements or other recruitment materials.

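### In Group 3 the uninjected fellow eye is not a valid same-visit control for acuity, because every pair sets an eye at 70 letters or more against one at 35 or fewer

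*Combined protocol and SAP*

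**What the plan says.** - **Section 6, Number of Subjects.** After the dose-escalation sample sizes, the text adds, in tentative terms, that they may be "sufficient to observe a treatment effect when compared in a matched fashion to the uninjected eyes in groups 1 and 3".
- **Section 3, Aim 3.** Group 3 subjects have "unilateral loss of acuity to ≤ 35 ETDRS letters" in one eye and good acuity, "≥ 70 letters (20/40 Snellen) in the contralateral eye (Group 3"), in the other. The choice of eye is fixed: "The eye with better acuity will be selected for injection".
- **Section 4, Background.** Loss may occur in both eyes at once, or "in one eye with the fellow eye affected weeks to months later".
- **Section 9, note to Table 6-6.** Group 3 has its own definition of a vision-related serious event, "due to the natural history of LHON where visual loss is expected in the asymptomatic eye". The injected eye is judged against the worst acuity recorded in its fellow.
- **Section 12, Data Analysis.** Acuity change is taken from Baseline 2, the planned statistics are descriptive, and changes in acuity are listed as ancillary. No paired efficacy estimand, alignment on time since onset, or baseline adjustment is given for Group 3.

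**The concern.** A fellow eye is a useful control when, without treatment, both eyes would be expected to follow the same course. In Group 3 the entry rules prevent that. The injected eye has not yet lost vision and is expected to; the control eye has already lost it. The eyes are matched on person but not on disease stage, their entry acuities cannot overlap, and the injected eye is not chosen at random.

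Two natural summaries then err in opposite directions. Paired change charges the expected second-eye loss to the vector. Paired acuity level credits the injected eye's head start to the vector. Because the plan does not say which summary the matched comparison would use, an inert vector could be reported as harmful or as protective. Section 3 makes a preliminary estimate of efficacy a further aim if Phase I supports it, and Section 12 looks to outcomes for later trials, so a misleading Group 3 signal could carry forward.

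**Working it through.** **1. The plan's own figure.** The Section 6 sentence refers to per-group sample sizes of N = 9, 12 or 15, with probabilities 20%, 54% and 22% at event rates of 0.05, 0.25 and 0.5. Exact enumeration of a 3+3 scheme (expand to 6 on 1 of 3, stop on 2 or more, then expand the next lower dose to 6 once) gives 19.7%, 53.7% and 21.6%. The figure reproduces. It describes escalation, however, and says nothing about whether the eyes are comparable.

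**2. Identity for one pair.** Let I0 and I1 be the injected eye's acuity at Baseline 2 and at follow-up, and F0 and F1 the fellow eye's.

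- Level difference: L = I1 - F1
- Change difference: C = (I1 - I0) - (F1 - F0)
- Therefore L - C = I0 - F0 = G, the baseline gap

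The Aim 3 entry limits give G of at least 70 - 35 = 35 letters. L and C cannot both be zero, whatever the vector does. This step needs no assumption about natural history.

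**3. Bias under no drug effect.** Suppose a share q of injected eyes falls to the fellow eye's average level, the rest do not change, and fellow eyes are stable. Then the expected C is -Gq and the expected L is +G(1 - q). The documents do not give q, so the whole range is shown at the minimum gap, G = 35:

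| q | Change difference (letters) | Level difference (letters) |
|---|---|---|
| 0 | 0 | +35 |
| 0.25 | -8.75 | +26.25 |
| 0.5 | -17.5 | +17.5 |
| 0.75 | -26.25 | +8.75 |
| 1 | -35 | 0 |

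As second eyes convert over follow-up, q rises. The level bias then shrinks while the change bias grows.

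**4. What a test would report.** An inert vector was simulated with N = 9 pairs (the Group 3 total in the Section 12 table) and two-sided 5% paired t-tests, 20,000 trials per setting. The assumptions, which are not from the documents, are injected-eye baselines of 70 to 85, fellow and post-loss levels of 5 to 35, and a measurement SD of 5 letters. The mean gap is then 77.5 - 20 = 57.5 letters.

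| q | Mean change difference | False harm on change | Mean level difference | False benefit on level |
|---|---|---|---|---|
| 0.25 | -14.5 | 16% | +43.0 | 96% |
| 0.5 | -28.9 | 68% | +28.6 | 63% |
| 0.75 | -43.2 | 98% | +14.4 | 18% |
| 1 | -57.5 | 100% | 0.0 | 2.6% |

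With SD 10 the results are similar: at q = 0.5, 63% false harm on change and 58% false benefit on level.

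**The case against.** The strongest reply concerns scope. The Section 6 sentence is a tentative aside in a paragraph on escalation. Section 12 plans descriptive statistics and specifies no paired test in Group 3. Its power tables already set 15-letter improvement against a natural-history rate, with tables labelled group 3 (33%, upper limit 70%). The Section 9 safety rule uses the fellow eye's worst acuity, so the authors saw the asymmetry. If nearly all second eyes convert, a late comparison of level has a null near zero.

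Most of this stands and limits the point. It does not remove it. The sentence still names group 3, and the safety rule is not carried over to efficacy. The group 3 power tables do not supply the expected course of a second eye either, because the text says the endpoint was assessed only on 31 worst eyes eligible for Aims 1 and 2. As q approaches 1, level becomes usable, but change from Baseline 2, the only acuity summary Section 12 names, is at its most biased.

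Four stronger readings are tempting, and the documents do not support them:

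- **That the fellow eye can never serve, at any sample size.** This holds only for simple pairing at the same visit. Aligning each eye on its own time since onset might work. The plan specifies no such comparison, and it would need first-eye acuities from before enrolment.
- **That Group 1 shares the flaw.** Both Group 1 eyes must be at 35 letters or fewer. Aim 1 does allow pairs that differ in time since onset (if "the difference in acuity between the eyes is ≤ 10 letters, the eye with ≥ 12 months will be injected"), but no figure shows that such eyes have different expected changes.
- **That the gap can be read against the 15-letter effect in Section 12.** That number is a responder threshold in a calculation on proportions; the gap is a paired difference in letters.
- **That the safety conclusions are compromised.** The toxicity endpoints and escalation do not rest on this comparison.

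**Conclusion.** The point holds for Group 3, and it is modest. As written, Section 6 offers a same-visit matched comparison whose two natural summaries must disagree by at least 35 letters when the vector does nothing. That figure follows from the entry limits alone. Eligibility is assessed before Baseline 2, so an individual Baseline 2 gap may differ somewhat through measurement variation.

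The direction and size of the bias depend on q: from 0 to -35 letters on change and from +35 to 0 letters on level, at the minimum gap. Those ranges assume stable fellow eyes and convergence to the fellow eye's level. False harm on change disappears at q = 0 and false benefit on level at q = 1; in between, both are present. Since the plan expects loss in the injected eye, the Baseline 2 change summary is the one most likely to mislead, and it does so towards harm. Only the exploratory efficacy reading of Group 3 is affected.

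**What to change.** 1. **Section 6:** delete 'and 3', so that the matched-comparison sentence refers to group 1 only.
2. **Section 12:** state that Group 3 efficacy will not be judged by simple fellow-eye pairing. Benchmark injected eyes against second-affected eyes of G11778A patients in the sponsor's completed natural history study who met the Group 3 entry acuities, aligned on time since first-eye onset. Section 24 already ties recruitment to that study ("This is the same strategy used to recruit patients for the completed natural history study"), and Section 22 describes a completed five-year LHON study with the same evaluations apart from the injection.
3. **Fallback:** if too few such eyes exist, report Group 3 acuity descriptively for each eye, with no efficacy claim based on the fellow eye.

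The cost is wording in two sections and reuse of existing data; no eligibility, dosing or safety rule changes. The downside is that Group 3 loses its within-patient control. The replacement may also be small: Section 24 gives more than 40 participants, but the documents do not say how many were second-eye converters meeting the Group 3 limits.

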A GLP compliant 1-month and 3-month dose based toxicity and biodistribution study of scAAV2-P1ND4v2 vector delivered by intravitreal injection into the eyes of normal rodents was performed at the University of Florida, Powell Gene Therapy Center Toxicology Core Facility.

The test article (vector) used in this study is the same as that planned for clinical investigation. The study consisted of 4 experimental groups. The animals were injected intravitreally with either Balanced Salt Solution (vehicle control group) or scAAV2-P1ND4v2 at a total dose of 6.56×10^6 , 6.56×10^7 and 1.97×10^8 vector genomes. Each arm consisted of 20 animals, which included 10 males and 10 females, half were sacrificed 30 days post injection and the remaining half were sacrificed 90 days post injection (+/-3 days). The primary safety endpoint of this study was the histopathology examination and biodistribution determination of the Skeletal muscle (quadriceps), Diaphragm, Heart, Cerebrum, Lung, Spleen, Liver, Kidney, Pancreas, Gonads, Jejunum, Parotid Gland, Mesenteric Lymph node, Un-injected eye with optic nerve (PCR only) and Injected eye with optic nerve (histopathology only). Clinical assessments were also measured by CBC and serum chemistry analysis. Clinical observations, including body weights, were also performed.

Intravitreal administration of vector genomes was well tolerated. There were no gross or microscopic findings that were related to administration of the test article. Daily clinical observations and weekly body weight measurements showed no test article-related trends.

Minimal test-article related clinical chemistry changes were observed in male rats in all vector dose groups, which was characterized by transient increases in alkaline phosphatase activity on Day 30. No vector or treatment related trends were seen in the complete blood count analyses. Vector genomes were not present in any non-target tissues and blood.

Safety Studies (Primate)

A 3-month dose based toxicity and biodistribution study of scAAV2-P1ND4v2 vector delivered by intravitreal injection into the eyes of normal non-human primates was performed at the Oregon National Primate Research Center at Oregon Health & Science University.

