We have shown that intravitreal injections of AAV serotype 2 efficiently transduces the cell type, retinal ganglion cells affected in LHON (Koilkonda et al 2014), that wild-type ND4 does not lead to ocular toxicity. In fact it prevents visual, RGC and optic nerve axonal loss due to the effects of an AAV carrying the mutant ND4 allele}

Our group has performed specific preclinical toxicology and biodistribution studies with intravitreal scAAV2-P1ND4V2.

5) Inclusion and Exclusion Criteria*

Subjects with LHON with the G11778A mutation confirmed by genetic testing during screening evaluation will be classified into three (3) groups based on long-standing (chronic), recent onset (acute bilateral) or acute unilateral (presymptomatic eye) disease manifestation.

The study population will include , males and females 15 years old or older diagnosed with G11778A-associated Leber's Hereditary Optic Neuropathy.

Inclusion Criteria

1. Age15 or older
2. Patients with LHON and the G11778A mitochondrial DNA mutation. A previous CLIA certified genetic lab result showing the LHON G11778A mutation will be accepted for inclusion;
3. Ability to perform tests of visual and retinal function;
4. Ability to comply with research procedures;
5. Able and willing to provide informed consent before undergoing any study related procedures.

6. Good general health as based on the investigator's assessment of the history, physical examination and laboratory testing performed at the baseline examination.

Exclusion Criteria

1. Unwilling or unable to give consent,
2. Unable or unlikely to return for scheduled protocol visits
3. Pregnant or nursing women or unwillingness for subject with childbearing potential to use contraception during the first year of the study.
4. Optic disc drusen on exam or in previous history.
5. Ocular diseases or visual dysfunction conditions other than refractive error (e.g. amblyopia, glaucoma, etc.) in the eye selected for the injection.
6. Previous eye surgery in the eye selected for injection.
7. Aspartate transaminase (AST)/alanine transaminase (ALT) $>5.0 \times$ upper limit of normal (ULN); Total bilirubin $>3 \times$ ULN; Hemoglobin $< 8 \text{ g/dL}$; neutrophil count $<1.0 \times 10^9/\text{L}$; or platelet count $< 50 \times 10^9/\text{L}$
 - a) Any laboratory screening test that meets the abnormality criteria stated above can be repeated once between Baseline one to Baseline 2.
8. Type I diabetes or the presence of diabetic retinopathy

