Systemic. Physical examination at regularly-scheduled time points will be performed by a medical practitioner to allow detection of and response to any acute symptoms. Complete blood count with differential, prothrombin time (with INR), partial thromboplastin time, serum chemistries, including measures of hepatocellular integrity and of renal function (including BUN and creatinine), and a urinalysis will be performed at baseline visit (serving also as a pre-injection evaluation) and on post-treatment evaluations. This testing will help detect toxicity in a number of organ systems. For research purposes measurements of neutralizing antibodies to human ND4 and AAV capsid components and cellular assays will be performed prior to and after vector administration as markers of the immune response. At each contact with the subject, information will be obtained on adverse events by specific questioning. Systemic toxicity will be graded based on the scale included in Table 6-6 and 6-7.

Table 6-6: Ocular toxicity scale

Toxicity	Grade 1	Grade 2	Grade 3	Grade 4
Keratitis (corneal inflammation / corneal ulceration)	Abnormal ophthalmologic changes only; intervention not indicated	Symptomatic ; medical intervention indicated	Symptomatic ; surgical intervention indicated	Perforation or blindness (worse than baseline visual function)*
Glaucoma	Elevated intraocular pressure (EIOP) warranting topical agent for intervention	EIOP requiring topical agents and oral agents for intervention	EIOP warranting operative intervention	EIOP uncontrolled, resulting in blindness (worse than baseline visual function)*
Cataract	Mild change from baseline, detected on ophthalmologic exam; not warranting intervention	Moderate change from baseline, detected on exam; not warranting intervention	Severe change from baseline, detected on exam; not warranting intervention	Severe change warranting operative intervention*
Uveitis	Mild anterior uveitis not warranting intervention	Moderate anterior uveitis warranting medical intervention	Severe posterior or pan-uveitis warranting medical intervention	Severe uveitis warranting operative intervention and threatening ocular integrity*
Vitreous hemorrhage	Mild hemorrhage detected on ophthalmologic exam; not warranting intervention	Moderate hemorrhage not warranting intervention	Severe hemorrhage warranting vitrectomy	Uncontrolled vitreous hemorrhage, threatening ocular integrity

Table 6-6: Ocular toxicity scale

Toxicity	Grade 1	Grade 2	Grade 3	Grade 4

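### Table 6-7 has no laboratory criteria, so a symptom-free laboratory abnormality defaults to Grade 1 or fits no grade, and cannot reach Grade 3

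*Combined protocol and SAP*

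**What the plan says.** Section 9 of the combined protocol and SAP (Study Endpoints, Systemic) schedules blood counts, clotting tests, liver and renal chemistries and urinalysis before and after injection, with the stated purpose of detecting organ toxicity. It then names the grading instrument: "Systemic toxicity will be graded based on the scale included in Table 6-6 and 6-7". Table 6-6 is the ocular scale, which leaves Table 6-7 for everything systemic. Its four grades are:

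- Grade 1: "Mild toxicity, usually transient, requiring no special treatment and generally not interfering with usual daily activities"
- Grade 2: "Moderate toxicity which may be ameliorated by simple therapeutic maneuvers, and impairs usual activities"
- Grade 3: "Severe toxicity which requires therapeutic intervention and interrupts usual activities", with hospital admission optional
- Grade 4: "Life-threatening toxicity which requires hospitalization"

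Section 9 cites CTCAE v3.0 only as the source of the ocular table. Numeric haematology and chemistry limits appear only as screening criteria, in exclusion 7 of section 5: AST/ALT above 5 x ULN, total bilirubin above 3 x ULN, haemoglobin below 8 g/dL, neutrophils below 1.0 x 10^9/L and platelets below 50 x 10^9/L. The sub-item attached to them also concerns screening only: "Any laboratory screening test that meets the abnormality criteria stated above can be repeated once between Baseline one to Baseline 2".

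The primary hypothesis in section 3 is that "there will be no systemic toxicity or loss of vision to No Light Perception in the injected eye".

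**The concern.** Hepatic, renal and haematological toxicity is often first seen as a laboratory value in a subject who feels well, and a panel repeated through follow-up is there to catch it. Table 6-7 instead asks whether the subject needed treatment, whether daily life was affected and whether admission was required. A laboratory value alone answers none of these, so the size of the abnormality does not enter the grade except through the opening adjective.

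What is at stake is the systemic safety summary. Two investigators could grade the same result differently, some events would have no grade to be tabulated under, and values serious enough to bar entry could appear in a table as mild. In Table 1 most cells hold three subjects, so one event graded differently moves the rate at that grade in its cell by 1/3, about 33 percentage points.

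A laboratory signal has some precedent here. The rodent study in section 4 reports "transient increases in alkaline phosphatase activity on Day 30" in male rats at every vector dose and attributes it to the test article. The protocol calls that change minimal and reports no test-article-related chemistry change in primates, so it shows only that a systemic signal may take laboratory form.

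**Working it through.** No calculated figure in the plan bears on this point. The check reads each grade in Table 6-7 as the set of conditions it states, and tests a laboratory abnormality that does not affect usual activities against each.

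**Step 1: conditions by grade**

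| Grade | Opening adjective | Treatment or admission | Usual activities | Laboratory value |
|---|---|---|---|---|
| 1 | mild | no special treatment | generally unaffected | none stated |
| 2 | moderate | simple measures may help | impaired | none stated |
| 3 | severe | treatment required | interrupted | none stated |
| 4 | life-threatening | admission required | no condition | none stated |

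**Step 2: laboratory findings without an effect on activities**

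| Case | Grade 1 | Grade 2 | Grade 3 | Grade 4 | Result |
|---|---|---|---|---|---|
| (a) Untreated | meets the treatment and activity conditions; only the word mild can object | fails on activities | fails on activities and treatment | fails on admission | Grade 1 by default |
| (b) Treated, not admitted | fails on treatment | fails on activities | fails on activities | fails on admission | no grade fits |
| (c) Life-threatening and admitted | fails | fails on activities as assumed | fails on activities as assumed | meets both conditions | Grade 4 |

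Cases (a) and (b) cannot reach Grade 3 as worded, however large the abnormality. In case (c) admission could itself be read as interrupting activities, but Grade 4 already applies.

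**Step 3: set against the entry limits.** Take each of the five limits in exclusion 7 and suppose it is crossed after injection, with no symptoms and no treatment. Each falls in case (a). So 5 of 5 values that bar entry would meet the treatment and activity conditions of the lowest grade if they arose on study.

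**Step 4: is there another laboratory rule?** A search of the supplied documents finds none for use after injection. CTCAE is adapted for the ocular table only. Section 14 lists clinically significant abnormal laboratory findings among the adverse events that can lead to withdrawal, but leaves this to the investigator's opinion. Sections 21 and 22 refer to a Manual of Procedures that was not supplied.

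**Step 5: compare with the ocular table.** In Table 6-6, Grade 3 cataract is a severe change from baseline found on examination that needs no intervention. There an objective finding is graded by its size against the subject's own baseline, without reference to treatment. Laboratory values are equally objective but have no such rule.

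**The case against.** The strongest reply is that each grade opens with an adjective, and Grade 1 adds that the toxicity is usually transient. An investigator need not call a transaminase value above 5 x ULN mild. That stands, and it is why the result in case (a) is a default and not a certainty. But an investigator who rejects Grade 1 has nowhere to go, because Grades 2 and 3 still fail on activities.

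Four stronger readings are tempting, and the documents do not support them.

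- *That any laboratory toxicity, whatever its size, is Grade 1, so the blood tests cannot register a severe event.* Treated findings leave Grade 1, and Grade 4 has no activity condition.
- *That under-grading would let the dose escalate.* Section 3 makes escalation depend on a major toxicity, which it does not define, and section 6 counts injected eyes that show the safety endpoint. Section 12 leaves continued recruitment to ongoing review by the Biostatistics Center and the monitoring committee. None of these refers to a Table 6-7 grade.
- *That the primary hypothesis would be upheld wrongly.* It speaks of no systemic toxicity, without a severity threshold, so a Grade 1 toxicity still counts against it.
- *That a dose trend would be invisible.* Clinical chemistry and haematology have their own datasets (section 12), so a trend can be read from the values.

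Safeguards outside the scale also count. An investigator reviews all laboratory results (section 10), systemic safety events are recorded and reported to FDA, NEI and the monitoring committee without a grade condition (section 12), and that committee reviews adverse events on an ongoing basis. These support detection. They rest on judgement and do not supply a reproducible grade.

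Finally, the Manual of Procedures may contain laboratory grades. If so, section 9 still names a different scale and needs a cross-reference.

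**Conclusion.** The point holds for grading and reporting. In the supplied documents the only systemic scale has no laboratory criteria, although laboratory tests are a main means of finding systemic toxicity. An abnormality without symptoms or treatment defaults to Grade 1, one treated without effect on activities has no grade, and neither can reach Grade 3. All five entry limits could be crossed after injection on those terms.

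This rests on two assumptions: that the conditions within each grade apply jointly, as the wording suggests, and that the unsupplied Manual of Procedures does not already fill the gap. The consequence is a systemic safety summary that depends on the grader and may be incomplete. An effect on dose decisions is not shown. The change is worth making, because the scale is unsuited to data the trial already collects throughout follow-up.

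**What to change.** In section 9:

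1. Grade every post-injection laboratory value on the laboratory tables of the CTCAE version that section 9 already cites for Table 6-6. If the Manual of Procedures already holds laboratory grades, cross-refer to it instead.
2. Report each subject's worst post-injection laboratory grade as a shift from that subject's own baseline grade.
3. Keep Table 6-7 for clinical signs and symptoms, and remove Table 6-6 from the sentence on systemic grading.
4. State that the higher of the laboratory and clinical grades is the subject's systemic toxicity grade.

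The CTCAE laboratory tables are not reproduced in the supplied documents, so the sponsor should confirm that they cover the analytes on the panel.

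The cost is one paragraph and one derived variable at the Biostatistics Center. No new tests are needed, and no treatment or dose rule changes. The downside is that more Grade 2-3 laboratory events will be listed, some unrelated to the vector; showing them as shifts from baseline helps the reader judge which matter.
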